3.2 Rationale of study design

The study is an open-label study where all patients will be receiving active study drug (zoledronic acid 0.05mg/kg).

Group 1: The Core study, CZOL446H2337, is part of a Pediatric Investigational Plan (EMA-000057-PIP01-07), [REDACTED]. This one-year study will extend the period of observation in patients who have completed the Core protocol and will collect long-term safety and efficacy data (Group1). The primary objective of the study will focus on general safety. The Extension study is an open-label study where all patients will receive active study drug (zoledronic acid 0.05 mg/kg). Given the rapid bone loss associated with the use of GCs and the fracture inclusion criteria for enrollment in the Core study, an open-label study design addresses ethical considerations for those patients who were randomized to receive placebo in the Core study who may deteriorate and require an active intervention, while at the same time allowing for the primary objective to be assessed.

Group 2: The study will capture additional safety and efficacy data on zoledronic acid from patients who presented with clinically significant back pain (significant symptoms) from vertebral fracture who were not enrolled into the Core study (Group 2) because the pre-existing clinical care at the Investigator's site is to treat this type of patient with a bisphosphonate.

3.3 Rationale of dose/regimen, duration of treatment

Zoledronic acid dose selection for Study CZOL446H2337E1 is based on several sources of information, including safety and efficacy data from completed Novartis clinical trials in adults with postmenopausal osteoporosis and GIO, pediatric patients with severe OI, long-term safety in pediatric patients with OI, and a PK study in pediatric patients with severe OI. Published data is available from trials in patients with postmenopausal osteoporosis (Reid et al 2002; Black et al 2007). Adults with benign disease (Paget's and PMO) have received safely up to 5 mg i.v. by slow injection (over 15 minutes) over various dosing frequencies. Cancer patients have received up to 4 and 8 mg i.v. monthly, in long term studies (> 1 year). In the zoledronic acid clinical development program in pediatrics to date, the dose selection was an infusion of 0.05 mg/kg (max 4mg) administered quarterly. This dose was extrapolated from a comparison with a pamidronate infusion in patients with tumor-induced hypercalcemia that showed that 4 mg zoledronic acid was more effective than 90 mg pamidronate. The 4 mg dose of zoledronic acid represents an approximate adult dose of zoledronic acid of 0.07 mg/kg or a dose of pamidronate of 1.5 mg/kg for a 60 kg adult. Pamidronate 1.5 or 3.0 mg/kg administered every 6 months was the dose range and interval used in the long-term pamidronate OI study (Glorieux et al 1998). In this pivotal trial, the pamidronate dosing interval was changed to an every 4 month dosing regimen as monthly evaluations of serum alkaline phosphatase concentration and urinary calcium excretion increased after 4 months.

The Study CZOL446H2202 is the largest NVS-sponsored trial in pediatric patients with metabolic bone disease. This 12-month study compared the efficacy and safety of i.v. zoledronic acid 0.05 mg/kg administered quarterly to i.v. pamidronate 1.0 mg/kg on each of 3

successive days administered quarterly in 155 patients with severe OI. The results showed that zoledronic acid was superior to pamidronate in increasing LS -BMD at month 12 and in reducing markers of bone turnover, both formation and resorption. [REDACTED]

[REDACTED] The overall incidence rate of adverse events was similar between the two treatment groups. There was no evidence of a long-term effect on renal function following the administration of zoledronic acid in this patient population. In addition to efficacy and safety evaluations, Study CZOL446H2202 assessed the pharmacokinetics of zoledronic acid. The pharmacokinetics of a single infusion of zoledronic acid 0.05 mg/kg, in children and adolescents aged 3-8 years and 9-17 years, were similar to those observed in adult oncology patients at approximately the same mg/kg dose. Plasma concentrations in the pediatric patients were generally at or below the median concentrations in adults, which may be an advantage in consideration of drug safety and tolerability in children. In a second trial with OI patients (Study CZOL446H2202E1), the 12-month Extension study to CZOL446H2202, long-term safety was assessed in 103 patients receiving 0.05 mg/kg zoledronic acid either as an annual infusion or twice yearly (6 months apart). In this study, median increases in LS-BMD were approximately 1.3% higher in patients who received the twice yearly dosing of zoledronic acid. Though these data from Study CZOL446H2202E1 should be interpreted with caution as the sample sizes are too small to make definitive conclusions, it is established that there is an effect of puberty on bone degradation, with children demonstrating high bone resorption relative to adults.

Therefore, the zoledronic acid dose and interval selected for the on-going Core protocol, 0.05 mg/kg as two i.v. infusions with a 6 month interval, is expected to provide superior efficacy (as measured by change in LS-BMD Z-score) compared to placebo in pediatric patients with osteoporosis. This same dose and regimen will be used into this protocol.

The maximum allowable zoledronic acid dose of 5 mg (regardless of patient weight), does not exceed the doses already used in adults and is well within the maximum zoledronic acid dose tested in Phase I Novartis Oncology trials: zoledronic acid 16 mg by slow i.v. infusion. In this study in children with secondary osteoporosis, zoledronic acid will be administered as at least a 30 minute i.v. infusion. Dose limitation and a 30 minute infusion time are designed to reduce the risk of possible adverse effects while maintaining efficacy.

3.4 Rationale for choice of comparator

No placebo-treatment arm will be used in this Extension study.

3.5 Purpose and timing of interim analyses/design adaptations

Not applicable.

3.6 Risks and benefits

Benefit

The potential benefit of zoledronic acid in children at risk of osteoporosis due to underlying disease or intermittent high dose GCs is outlined in [Section 1.1](#) and in the Investigator's Brochure.

[REDACTED]

Additional evidence suggests that bisphosphonates have anti-apoptotic effects on osteoblasts and osteocytes which may lead to increased trabecular thickness and thus, may partly explain why bisphosphonates produce a greater reduction in fracture risk than that expected from BMD gains alone (Plotkin 1999).

The skeletal toxicity of GC is confirmed in adults and children. Furthermore, BMD is greatly influenced by sex steroids, and puberty can be delayed in the presence of GC which can also result in short stature which may be offset by the use of bisphosphonates (Glorieux et al 1998).

Risks

Known risks of zoledronic acid

Since this protocol was first written in 2010, there have been more publications on the potential use of bisphosphonates in children with kidney diseases including nephrotic syndrome (Gruppen et al 2013, Sbrocchi et al 2011).

Zoledronic acid is concentrated and excreted via the kidney and, like other bisphosphonates, has the potential to produce renal injury. Thus, care should be taken when administering the compound to patients with renal insufficiency. Although case reports have been published in adults regarding the nephrotoxicity of zoledronic acid with an incidence of acute kidney injury (AKI) between 9% and 13%, bisphosphonate-induced AKI in children remains undocumented (Patzer 2008).

- In this protocol, patients are excluded if they have an estimated glomerular filtration rate (GFR) < 60 ml/min/1.73 m². In addition patients considered for Group 2 who have nephrotic syndrome with osteoporosis, who do not meet this exclusion criterion, have been stable for 3 months prior to enrollment, and meet the remaining eligibility criteria, can be considered for this study.

Post-infusion acute phase reactions are more common after the first infusion and can include pyrexia, muscle and joint pain,

- To reduce the risk of these reactions, children will be instructed to eat and drink as usual, NSAIDs or acetaminophen (paracetamol) will be prescribed and an anti-emetic may be provided to reduce the risk of symptomatic hypocalcemia if the child develops nausea or starts to vomit. Further calcium supplements will be provided for up to 10 days at the time of infusion and parent/legal guardian instructions provided on the signs to watch for as well as an emergency number, if needed.

A rare risk in patients who receive bisphosphonates is osteonecrosis of the jaw (ONJ). This condition has been reported in cancer patients whose complex treatment regimens include higher doses and frequencies of bisphosphonates, typically administered with other treatments such as radiation, chemotherapy and GCs. To date, ONJ has not been reported in the literature in children or adolescents who have received bisphosphonates. Based on available evidence, a causal relationship between ONJ and bisphosphonates, including ZOL, has not been established.

- In this study a lower dose and short duration of zoledronic acid is used than has been reported in cases of ONJ in adults, and all children will have an examination of their oral cavity during the study and referred to a dentist if necessary.

Potential risks of zoledronic acid in a pediatric population

Based on the results from animal studies showing inhibition of bone calcification by first generation bisphosphonates (Mashiba et al 2000), there are theoretical concerns about negative effects on growth in children. In growing children, each bisphosphonate treatment cycle leads to the accumulation of a thin band of mineralized tissue at the interface between growth plate and metaphysis which is evident as a metaphyseal line on the radiograph (Land et al 2006a). These lines represent persistent calcified cartilage in the horizontal trabeculae which later remodels into secondary bone. This interface between weaker bone and stronger bisphosphonate-treated bone could represent a site for potential fracture. However, in clinical trials with i.v. bisphosphonates, linear growth in children and adolescents has not been observed to be negatively impacted with no observed increase in fracture. To the contrary, cyclical i.v. treatment with pamidronate has been shown to be beneficial in children with severe forms of OI (Glorieux et al 1998).

- To investigate this potential risk, all subjects will have DXA examination at 6 and 12 months and in the event of clinical worsening or diagnosis of new fracture, an X-ray will be performed.

Another concern in children is effects on the reproductive organs. The animal reproduction studies of zoledronic acid are described in [Section 4.3.5 of the Investigator's Brochure]. Teratogenicity was observed in the rat, but not the rabbit when treatment during the perinatal period resulted in delayed parturition likely resulting from the calcium lowering effect of the compound outside of bone, which negatively affects uterine contraction. There were no effects reported in males.

- Consequently this protocol requires contraception in all girls who are pubertal and may become pregnant and in some countries additional pregnancy checks will be made.

There are potential concerns regarding the i.v. infusion in children. Apart from the potential risks at the infusion site of pain, infection, phlebitis, hematoma and extravasation, the infusion may also cause fluid overload if the rate is too high and this can result in hypertension, heart failure or pulmonary edema. Additional risks of the infusion can include electrolyte imbalance and embolism.

- The infusion is administered in a hospital or clinic by staff experienced in administering i.v. infusions to children. The infusion line is flushed with saline before and after administration and the infusion given over at least 30 minutes e.g. in a 25 kg child, 100 mL may be administered over one hour at a rate of 5 mL/minute.

Protocol procedures: blood draws and radiology

The number of blood draws and frequency of hospital visits in this protocol is within the usual limit of clinical practice for children with these serious underlying diseases. The radiation exposure is increased over routine clinical practice, but within the limits for children who have suffered a fracture and no greater than the exposure during a transatlantic flight. Repeat blood draws and X-rays/DXA will only be requested when absolutely necessary i.e. safety, baseline or end-of-study visits.

In summary, the risks to the children and adolescents in this trial will be minimized by compliance with the eligibility criteria and study procedures, particularly adequate hydration at the time of the infusion, adherence to a diet rich in calcium and vitamin D, regular renal

monitoring and contraception in girls of child bearing potential. A maximum dose of 5 mg zoledronic acid (regardless of patient weight) and a minimum 30 minute infusion time 6 monthly are designed to reduce the risk of possible adverse effects. This dose regimen has been used in children with primary and secondary osteoporosis and has shown a favorable risk-benefit profile.

4 Population

Group 1: Patients who have received at least one dose of study drug, have completed participation in the Core study and who meet the inclusion/exclusion criteria for this extension, will be eligible to participate. These patients have been previously diagnosed with non-malignant conditions (including but not limited to rheumatologic conditions, IBD, DMD, nephrotic syndrome) and have been treated with systemic GCs (i.v. or oral) prior to the Core study and have evidence of at least 1 vertebral compression fracture confirmed by central reading or one or more low-trauma lower extremity long bone fractures or two or more low trauma upper extremity long bone fractures confirmed by radiology report.

Group 2: Patients who were not eligible for the Core study because of clinically significant back pain from vertebral fracture and the preexisting clinical care at the Investigator's site is to treat this type of patient with a bisphosphonate.

Approximately 100 patients will be eligible for enrollment into the extension, for both groups. Patient recruitment in Group 2 will stop once enrollment in the Core study is completed

4.1 Inclusion criteria

Patients eligible for inclusion in this study have to fulfill all of the following criteria:

- Written informed consent must be obtained before any assessment is performed. An assent needs to be provided in accordance with ICH and local regulations.

Group 1:

1. Children and adolescents, male or female, between 6 to 19 years of age who met the inclusion criteria for entry into the Core study and who took at least one dose of study drug and have completed Visit 8 of the CZOL446H2337 Core study.
2. Patient must be enrolled into the extension at Visit 9 up to 10 months after Visit 5 (month 6) of the Core study.
3. Patients who followed the regimen of calcium and vitamin D intake as required in the Core study (at least 1000 mg calcium for 6-8 years of age or at least 1300 mg calcium for 9-19 years of age and at least 600 IU daily vitamin D, through diet or supplementation).

Group 2:

1. Children and adolescents, male or female, between 5 to 17 years of age who met the inclusion criteria for entry into the Core study but were not enrolled because of clinically significant back pain from vertebral fracture and the preexisting clinical care at the Investigator's site is to treat this type of patient with a bisphosphonate.
2. Confirmed diagnosis of non-malignant conditions (including but not limited to rheumatic conditions, inflammatory bowel disease, Duchenne muscular dystrophy, nephrotic syndrome) who have stable normal renal function for at least 3 months prior to screening or

other subtype of secondary osteoporosis in children taking GCs, except patients with oncologic conditions (such as lymphoma and leukemia) see [Appendix 6](#)), treated with systemic GCs (i.v. or oral) within the 12 months preceding enrollment in the study (any duration)

3. Lumbar Spine areal BMD Z-score of - 0.5 or worse confirmed by central imaging
4. Evidence of at least 1 vertebral compression fracture (at least Genant Grade 1 vertebral compression or radiographic signs of vertebral compression*) seen on X-ray within 1 month of or at screening visit confirmed by central reading.

*Radiographic signs of vertebral compression fracture include loss of endplate parallelism, vertebral buckling and endplate interruption.

4.2 Exclusion criteria

1. Patients who demonstrated a major protocol violation in the Core study (Group 1 only)
2. Patients for whom the investigator considers participation in the Extension study is not appropriate (Group 1 only).

(For both groups)

3. Hypocalcaemia and hypophosphatemia: any value (age-matched) below the normal range at Visit 8 or 8 A.
4. Vitamin D deficiency (serum 25-hydroxy vitamin D concentrations < 20 ng/mL or < 50 nmol/L) at Visit 8 for Group 1, Visit 8 A for Group 2.
5. Local serum ionized calcium below the normal range at Visit 9.
6. Renal impairment defined as an estimated GFR < 60 ml/min/1.73 m² based on the Schwartz formula at screening Visit 8 or 8 A (in the case of DMD additional methods may have been recorded in the source documents). Serum creatinine above the normal range at Visit 9 (Group 1) or an increase between Visit 8 A and Visit 9 greater than 0.5 mg/dL (44.2 μ mol/L) for Group 2.
7. Uncontrolled symptoms of cardiac failure or arrhythmia
8. Any prior use of bisphosphonates (other than study drug during the Core study for Group 1 only) or sodium fluoride (doses for osteoporosis not for dental hygiene).
9. Current active hyperparathyroidism or hyper/hypothyroidism or during the Core study.
10. New diagnosis of sarcoidosis currently or during the Core study.
11. New malignancy diagnosis currently or during the Core study.
12. History of hypersensitivity to any of the study drugs or to drugs of similar chemical classes.
13. History of primary bone disease (OI, idiopathic juvenile osteoporosis, rickets/osteomalacia).
14. Female patients of child bearing potential are eligible only if they are: (1) not pregnant/non-lactating; (2) are sexually abstinent or are surgically sterile or (3) if sexually active, must be practicing a medically acceptable form of birth control for greater than 2 months prior to screening visit.

- Females of child bearing potential who are sexually active must agree to continue to practice their birth control during the trial and at least 1 year after completing the trial and must consent to a pregnancy test prior to every dose administration and at the End of Study (EOS) Visit.
- [For sites where additional safeguards are required only: Female patients of child bearing potential are eligible only if they are not pregnant/non-lactating. Females of child bearing potential must be practicing a medically acceptable form of birth control for greater than 2 months prior to screening visit. At least one and preferable two complementary forms of contraception including a barrier method should be used and be continued throughout the trial and for at least 1 year after completing the trial. They must also consent to a pregnancy test prior to every dose administration and at the EOS visit. An additional supervised urine pregnancy test will be assessed at Visit 11 (Month 15) (See [Section 6.5.5](#)).

No additional exclusions may be applied by the investigator, in order to ensure that the study population will be representative of all eligible patients.

5 Treatment

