6.5.4.2 Clinical chemistry

Non-fasting specimens will be obtained for glucose, creatinine, serum urea, uric acid, total protein, SGOT (AST), SGPT (ALT), alkaline phosphatase, sodium, potassium, chloride, phosphorus, magnesium, albumin, total bilirubin, gamma-glutamyl transpeptidase (GGT) and calcium.

Glomerular Filtration Rate (GFR) will be calculated using the Schwartz equation at all visits where serum creatinine will be measured (Visits 8A (Group 2 only) 9, 10, 12, 13 and 15) by the Central Laboratory.

Schwartz Formula to calculate Glomerular Filtration

$GFR (mL/min/1.73 m^2) = k [Height (m)] / Serum Creatinine (mg/dL)$

k = Constant

k=0.41

Specialized (non-fasting) testing for serum 25-hydroxy vitamin D will be performed at Visit 8/8A and Visit 15. Additional local laboratory evaluation of serum ionized calcium will be evaluated in the local laboratory at pre-dose (first infusion). If local serum ionized calcium at Visit 9 is less than the normal range, the infusion must not be given. The patient may retest once at the investigator's discretion. If the serum ionized calcium retest is in the normal range, the patient may be dosed.

Also, local laboratory evaluation of serum creatinine will be performed at Visit 8A (Group 2 only) and Visit 9 for exclusion purposes. If local serum creatinine at Visit 9 is less than the normal range, the infusion must not be given. The patient may retest once at the investigator's discretion. If the serum creatinine retest is in the normal range, the patient may be dosed.

Patients with laboratory tests containing clinically significant abnormal values will be followed regularly until the values return to normal ranges or until a valid reason for the abnormality, other than study drug related adverse event, is identified

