### **Laboratory parameters**

The summary of laboratory evaluations will be presented with respect to three groups of laboratory tests (hematology, serum chemistry, and urinalysis).

- Hematology parameters: hemoglobin, hematocrit, platelet count, red blood cell count (RBC), mean cell volume (MCV), mean cell hemoglobin concentration (MCHC), RBC morphology, white blood cell count (WBC) and differential white blood cell counts.
- Serum chemistry parameters: non-fasting glucose, creatinine, serum urea, uric acid, total protein, SGOT (AST), SGPT (ALT), alkaline phosphatase, sodium, potassium, chloride, phosphorus, magnesium, albumin, total bilirubin, gamma-glutamyl transpeptidase (GGT), calcium; and Glomerular Filtration Rate (GFR).
- Urinalysis parameters: amorphous crystals, urine bilirubin, urine blood, calcium oxalate crystals, urine color, urine glucose, urine ketone, urine leukocytes, urine

nitrite, pH, urine protein dipstick, specific gravity, urine urobilinogen, and WBC Casts (Urine) /LPF.

GFR will be calculated using the Schwartz equation at all visits where serum creatinine will be measured (Visits 9, 10, 12, 13 and 15) by the Central Laboratory.

$GFR (mL/min/1.73 m^2) = k[Height (m)]/Serum Creatinine (mg/dL)$ , where  $k=0.41$

Descriptive summary statistics for both baselines, each post-baseline visit, and change from both baselines to each visit will be presented by laboratory test group and core treatment group. Note that if either the baseline or the post-baseline value is missing, then the calculation of change from baseline will also be missing.

Also, shift tables for hematology and serum chemistry will be provided in order to compare a patient's baseline laboratory evaluation relative to each study visit. For the shift tables, the normal laboratory values will be used to evaluate whether a particular laboratory test value is normal, low, or high for each visit value relative to whether or not the baseline value is normal, low, or high. These summaries, including changes from both baselines, will be presented by laboratory test group and core treatment group.

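### Renal laboratory limits rest on creatinine in every patient, and the SAP does not report renal results separately for Duchenne patients, in whom those limits may be less sensitive

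*Protocol*

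**What the plan says.** Protocol section 4.2, criterion 6, sets one screening limit for all patients: "Renal impairment defined as an estimated GFR < 60 ml/min/1.73 m² based on the Schwartz formula at screening Visit 8 or 8 A". At Visit 9 it adds a creatinine check that differs by group: "Serum creatinine above the normal range at Visit 9 (Group 1") for one, and "an increase between Visit 8 A and Visit 9 greater than 0.5 mg/dL" for Group 2. The only reference to DMD is the parenthesis "in the case of DMD additional methods may have been recorded in the source documents". It names no method, gives no reason, and does not say how a result would be used.

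Section 6.5.4.2 gives a single formula, "k [Height (m)] / Serum Creatinine (mg/dL"), with k = 0.41 for every patient. The central chemistry panel includes creatinine and urea but no filtration marker independent of creatinine. Table 13-1 (Appendix 1) makes creatinine notable when it lies outside an age and sex range, on either side, with no separate range for DMD.

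The SAP, under Laboratory parameters, repeats the equation: "GFR will be calculated using the Schwartz equation at all visits where serum creatinine will be measured". It summarises values and changes from both baselines by core treatment group. Newly notable values are counted only in patients whose baseline is normal or missing. Under Adverse events, by contrast, all adverse events are also tabulated by underlying disease group.

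The protocol explains why renal results matter: "Zoledronic acid is concentrated and excreted via the kidney and, like other bisphosphonates, has the potential to produce renal injury" (section 3.6). Section 9.4.1 names renal safety for particular attention.

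**The concern.** Serum creatinine depends on how much creatinine is produced as well as on how well the kidney clears it. If production is low, a formula of the form constant × height / creatinine reads high, and an age-based upper limit is reached late. The DMD parenthesis suggests that the authors doubted the formula alone in that disease. Yet the alternative results enter no rule, no schedule and no table.

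At stake is the sensitivity of the renal part of the primary safety analysis in one identifiable stratum. A renal decline in a low-creatinine child could stay inside every absolute limit and then be averaged into tables that do not show the stratum. The newly-notable rule adds a second gap. A child whose creatinine starts below range has an abnormal baseline, so that table omits the child even if creatinine later rises above range.

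**Working it through.** The plan states no figure to reproduce, so this is direct arithmetic.

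**Inputs from the documents.** k = 0.41 (section 6.5.4.2); GFR limit 60 (section 4.2); male creatinine ranges in mg/dL from Table 13-1: 0.2–0.5 (5–7 years), 0.3–0.6 (>7–10), 0.3–0.7 (>10–13), 0.4–0.8 (>13–16), 0.5–0.9 (>16–20).

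**Assumptions.**
- Height is in cm. Both documents print metres, which gives 0.41 × 1.4 / 0.7 = 0.82, so every patient would fall below 60. That is a separate error to reconcile; the present point remains after it is corrected.
- Heights are illustrative, 105–175 cm across the age bands.
- The Visit 9 normal range equals Table 13-1. That check uses a local laboratory, whose range may differ.
- Creatinine at a given true GFR is f times that of a typical child. The documents give no value; 0.3 to 0.8 is shown.

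**Step 1: which limit binds in Group 1.** Formula GFR equals 60 at creatinine = 0.41 × height / 60. This is 0.72–0.85 mg/dL at 5–7 years (105–125 cm), 0.85–1.06 at >10–13 (125–155 cm) and 0.99–1.20 at >16–20 (145–175 cm). All exceed the upper limits of 0.5, 0.7 and 0.9. The creatinine check therefore binds before the GFR limit.

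**Step 2: formula GFR at the upper creatinine limit.** 0.41 × 120 / 0.6 = 82; 0.41 × 140 / 0.7 = 82; 0.41 × 160 / 0.8 = 82.

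**Step 3: true GFR at that point = f × 82.**

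| f | True GFR |
|---|---|
| 0.3 | 25 |
| 0.5 | 41 |
| 0.7 | 57 |
| 0.8 | 66 |

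A true GFR below 60 passes only if f < 60 / 82 = 0.73. Over all the heights and age bands tested, this break-even value runs from 0.59 (5–7 years, 125 cm) to 0.91 (>16–20 years, 145 cm).

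**Step 4: room inside the range, without f.** A boy who starts at the lower limit can lose 1 − lower/upper of his formula GFR, at constant height, before creatinine leaves the range: 60%, 50%, 57%, 50% and 44% in the five bands. This holds for any child, but matters most where low starting values are common.

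**Step 5: what removes f.** Displayed GFR is true GFR / f. Absolute change in displayed GFR is therefore scaled by 1/f, and absolute change in creatinine by f. In percent change f cancels, provided it is stable. If f drifted from 0.8 to 0.7, an unchanged GFR would read 0.8 / 0.7 = 1.14 times its baseline, so percent change reduces the dependence but does not abolish it.

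**The case against.** The strongest reply is that the premise comes from outside the documents. Neither says creatinine is low in DMD; the only DMD laboratory effect described is raised AST and ALT from muscle breakdown (Amendment 3 rationale). That stands, so the size can only be conditional on f.

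Much is also already covered. The SAP gives change from both baselines, shift tables and flagged patient listings. Urea and urinalysis are collected. Section 7.1 asks investigators to review significant changes from baseline and values atypical for the underlying disease. Renal adverse events have a Cox model with underlying condition and an interaction term. Group 2 has a within-patient creatinine rule, and criterion 2 allows investigator judgement in Group 1. All of this stands, and a low-to-high creatinine shift would appear in the shift table. But none of the laboratory summaries separates DMD, and change is not expressed in percent.

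Three stronger readings are tempting and are not supported:
- **That the plan admits Group 1 children with a true GFR of 18–48** (60 × 0.3 to 60 × 0.8). Step 1 shows that the GFR limit of 60 is not the binding one there.
- **That the additional DMD results are already on file for all.** The clause says only that they may have been recorded. Whether the eCRF holds them cannot be judged from these documents.
- **That arm comparisons of mean GFR are distorted by differing DMD shares.** The SAP calls underlying condition a stratification factor, which limits imbalance. Selection into the extension could leave some, but no DMD count is given.

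**Conclusion.** The point holds as a reporting gap and a possible loss of sensitivity. It is not evidence that impaired patients are being missed. Absolute renal limits rest on creatinine in all patients, the DMD parenthesis has no consequence anywhere, and the renal laboratory tables do not separate a stratum that the adverse event tables do. In the worked example a true GFR below 60 passes the Group 1 limits only if f is below about 0.73 (0.59 to 0.91 over the heights and bands tested); at f = 0.8 the example gives 66 and there is no miss. These figures rest on the assumed f, illustrative heights in cm, and the Table 13-1 ranges.

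The newly-notable table's omission of children who start below range follows from the SAP's own rule and needs no assumption about f. How many children it affects is unknown. The change is worth making because it is cheap, not because the primary analysis fails without it.

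**What to change.** In the SAP, under Laboratory parameters:

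1. Present creatinine, GFR and renal notable-value tables for DMD and non-DMD within core treatment group.
2. Add within-patient percent change in creatinine and GFR from both baselines.
3. Report separately any patient whose creatinine is below range at baseline and later above range, since the newly-notable count leaves such patients out.
4. List additional DMD renal results where they exist, stating for how many patients they are available.

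The first three items use variables already held and cost a few extra tables. The fourth may need transfer from source documents and may be incomplete. The DMD stratum may be very small, so its tables should be read descriptively beside the patient listings. The SAP covers only patients who completed the Core study; the same display would be needed wherever Group 2 is reported.

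The sponsor should also reconcile the DMD parenthesis with the rest of criterion 6. Section 6.5.4.2 and criterion 6 disagree on whether a Visit 9 creatinine below or above range is the bar, which bears directly on low-creatinine patients, and these passages must be reconciled too. No eligibility rule, test or threshold is proposed here.
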